#### 8.4 Adjudication committee

#### Clinical endpoint committee

All clinical events, which could potentially fulfill the Category 1 or 2 endpoints will be assessed during the study and reported to the Clinical Endpoint Committee for adjudication.

The CEC will review and adjudicate events including but not limited to deaths (CV and non-CV death), circulatory and/or respiratory mechanical assistance for life support, listing for heart transplantation, and clinical worsening of heart failure (with or without hospitalization) for endpoint determination. The detailed definitions of the endpoints, required documentation, and the adjudication process will be included in a separate CEC Manual.

Sites are instructed to take a conservative approach when reporting endpoints. If the Investigator suspects an endpoint may have occurred, it is best to report the event in the endpoint CRF.

#### Angioedema adjudication committee

If an angioedema or angioedema-like event occurs, the Investigator will complete case report forms for angioedema adjudication. Details on the process of reporting angioedema and angioedema-like events are outlined in a manual provided to Investigators.

Submission of an angioedema report is not a substitution for the submission of an SAE report. If an angioedema-like event satisfies the definition of an SAE, the Investigator must submit an SAE report in addition to the adjudication report for an angioedema-like event.

The membership and responsibilities of the Angioedema Adjudication Committee are defined in a separate document that will be provided to the sites.

#### 8.5 Part 1 PK/PD data review

As described in Section 3.1, the age groups will be enrolled sequentially from Group 1 to Group 3. For the oldest age group (Group 1: 6 to < 18 years), the PK, PD, and safety data obtained from all 12 observations will be reviewed by the DMC prior to starting Group 2 in Part 1 and

to support the dose recommendation before patients will be enrolled into Part 2 of the same age group. Similarly, for Group 2 (1 to < 6 years), the PK, PD, and safety data obtained from all 12 observations will be reviewed by the DMC prior to starting Group 3 in Part 1 and to support the dose recommendation for Part 2 of the same age group. For Group 3 (1 month to < 1 years) the PK, PD, and safety data obtained from approximately 8 observations will be reviewed by the DMC to support the dose recommendation for Part 2 in the same age group. All suspect abnormalities will be discussed before enrollment into the next dose group/age group is allowed. The decision on the dosing for Part 2 (Efficacy) for each age group will be made jointly by Novartis and the DMC.

Data review is anticipated to include the following, when available:

- AEs and SAEs and their causal relationship to the study drug
- Evidence of pharmacodynamic interactions between LCZ696 and co-medications
- Vital signs
- Blood chemistry and hematology
- PK and PK/PD response

### 9 Data analysis

The analysis will be conducted on all subject data at the time the trial ends. Any data analysis carried out independently by the Investigator should be submitted to Novartis before publication or presentation.

### 9.1 Analysis sets

For Part 1: All subjects with at least one dose of study drug will be included in safety analysis set. All subjects with evaluable PK/PD data will be included in the PK/PD data analysis.

For Part 2 (Efficacy), the following populations will be used for the statistical analyses

The full analysis set (FAS) will consist of all randomized patients with the exception for those patients who have not been qualified for randomization and have not received study drug, but have been inadvertently randomized into the study. Following the intent-to-treat principle, patients will be analyzed according to the treatment to which they were assigned at randomization. Efficacy variables will be analyzed based on the FAS as the primary population.

The Safety Population (SAF) will consist of all patients who received at least one dose of study drug and have at least one post-baseline safety assessment. Of note, the statement that a patient had no AEs also constitutes a safety assessment. Patients will be analyzed according to the treatment actually received. The safety population will be used for the analyses of safety variables.

The Per-Protocol (PP) population will be a subset of the FAS which will consist of the patients who do not have major deviations from the protocol procedures in the double-blind study stage. Major protocol deviations will be pre-specified prior to unblinding treatment codes for analyses. This supplemental efficacy population will be used to support the primary analysis results.

#### 9.2 Patient demographics and other baseline characteristics

Summary statistics for Part 1 (PK/PD) and Part 2 (Efficacy) will be provided by treatment group for demographics and baseline characteristics, including age, age group (Group 1: 6 to < 18 years; Group 2: 1 to < 6 years; Group 3: 1 month to < 1 year), modified age group (Group 1: 6 to < 18 years; Group 2a: 2 to < 6 years; Group 3a: 1 month to < 2 years), sex, race, ethnicity, weight, height, body mass index (BMI), category of prior HF medication, HF etiology, prior HF hospitalization, NYHA/Ross class, and vital signs. BMI will be calculated as weight (kg) / height² (m²) from the collected height and weight at the Screening visit. Continuous variables will be summarized using n, mean, standard deviation, median, minimum, and maximum. Categorical variables will be summarized using frequency and percentage. Additionally, summary statistics will be provided by treatment and age group, and by treatment and modified age group, for demographics and baseline characteristics for both Part 1 and Part 2.

For Part 2 (Efficacy), baseline value is defined as the last non-missing assessment prior to the first dose of randomized study medication unless specified otherwise.

For Part 1 (PK/PD), all subjects with at least one dose of study drug will be included in the above analyses. For Part 2 (Efficacy), the FAS set will be the patient population for the above analyses.

#### 9.3 Treatments

#### Part 1 (PK/PD)

The study drug administration (single dose of LCZ696 in mg/kg) will be summarized for subjects who received study drug during Part 1 (PK/PD). The summary will be conducted by age group and overall; and the summary will use mean, standard deviation, median, minimum, and maximum. The number and percentage of patients will be summarized by age group and dose levels (mg/kg).

Concomitant medications will be summarized by therapeutic class, preferred term (PT) and dose level for each age group and overall for all subjects who received study drug in Part 1 (PK/PD).

#### Part 2 (Efficacy)

The overall duration of the double-blind study drug will be summarized for the SAF population by treatment group using mean, standard deviation, median, minimum, and maximum. Additionally, the number and percentage of patients will be summarized by treatment group for duration category.

Concomitant medications will be summarized by therapeutic class, preferred term (PT), treatment group for the SAF population.

Additionally, all analyses conducted above for Part 2 (Efficacy) will be summarized by modified age group.

### 9.4 Analysis of the primary variable(s)

#### 9.4.1 Variable(s)

#### Part 1 (PK/PD)

The objective of Part 1 of the study is to characterize PK and PD of LCZ696 in pediatric patients and compare PK, PD, and exposure-response with observed data in adult heart failure patients in order to determine the dose for Part 2 (Efficacy) of the study. In Part 1 (PK/PD) of the study, the pediatric patient population is divided into three age groups; Group 1: 6 to < 18 years old, Group 2: 1 to < 6 years old, and Group 3: 1 month to < 1 year old.

Considering various factors including factors such as ontogeny of enzymes/transporters, the variability in PK parameters is assumed to be similar between adult and pediatric HF patients (>3 months). Since LBQ657 is a metabolite, clearance and volume of distribution were not estimated in earlier clinical trials and coefficient of variation% (CV%) of total exposure was considered for sample size estimation. From previous clinical study in adult HF patients, the observed CV% for body-weight normalized LBQ657 exposure was 37.1% and the observed CV% for body-weight normalized clearance and volume of distribution of valsartan was 39.4% and 49.6%, respectively (CLCZ696A2117). Therefore 49.6% of CV% was assumed for sample size estimations. The sample size is up to 12 observations per age group (except Group 3 where N= 8 observations) to achieve 95% CI for geometric mean of PK parameters to fall between 60% and 140% range (95% CI: 71 – 141%) with 80% coverage probability.

A population PK model will be developed to describe incoming data from pediatric patients based on an established model developed for the adult HF population. The fidelity of the developed PK model will be cross validated for its robustness and precision to the observed data. The steady state population PK parameters including clearance, volume of distribution, Ka, T1/2, Cmax, Cmin, and AUC will be estimated. The impact of covariates such as eGFR, age, body weight, NYHA/Ross class, TBL, and AST levels will be evaluated.

Pharmacodynamic evaluations will include analysis of change in plasma cGMP, plasma BNP, plasma NTproBNP and urine cGMP. Dose and exposure-response relationship will be evaluated based on changes in plasma cGMP levels (and also plasma NTproBNP, plasma BNP, urine cGMP).

PKPD modeling of Part 1 data may be carried out, depending on the robustness of both the PK and biomarkers to be used to inform the dose justification for Part 2.

#### Part 2 (Efficacy)

The global rank primary endpoint is constructed through 2 steps:

- Step 1: Patients are classified into the 5 ordinal categories based on the logic described in Table 6-3 in Section 6.4.1.
- Step 2: Within each category, patients are ranked from worst to best based first on the subcategory if applicable, and then the ranking algorithm as explained in Table 6-3.

#### 9.4.2 Statistical model, hypothesis, and method of analysis

The primary endpoint comparing the distributions for patients receiving LCZ696 and patients receiving enalapril will be assessed using a stratified Wilcoxon rank-sum analysis (Kawaguchi 2011), stratifying by modified age group (Group 1: 6 to < 18 years; Group 2a: 2 to < 6 years; Group 3a: 1 month to < 2 years) and NYHA/Ross class group (Class I/II; Class III/IV). The overall significance level (Type 1 error) of 0.05 (2-sided) will be used. In addition, the proportion of patients falling into each of the 5 ordered categories of the primary endpoint will be presented by treatment group. These proportions will be provided both hierarchically (only worst category counted for each patient), as the endpoint is defined, and overall, not accounting for whether a patient also had a worse event. Full analysis set will be used for these analyses.

In addition, the number and percentage of patients in each category will be provided by treatment group for each age group, each modified age group, and for overall.

Due to unresolvable technical reasons in study drug supply, the unforeseen intercurrent events of the USM leading to study treatment discontinuations are not related to disease progression, are not related to the assigned study treatment, and do not reflect a real-world setting. The exposure to the study treatment and study follow-up are reasonably long. Therefore, the ontreatment approach is considered to be more appropriate for the handling of USM-impacted patients in the primary analysis, utilizing the relevant components of the global rank endpoint including Category 1 and Category 2 status at the time of treatment discontinuation.

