#### Amendment rationale

The main reasons for this amendment are as follows:

- Based on review of Part 1 Age Group 3 PK/PD/Safety data, this amendment defines the target dose and dose regimen for Part 2 Age Group 3 to enable enrollment into Part 2 for Age Group 3. The planned target dose of LCZ696 2.3 mg/kg bid for Part 2 Age Group 3 together with the implementation of additional hypotension safety monitoring for Part 2 Age Group 3 during the initial up-titration phase is supported by the DMC and has been added to the protocol with this amendment. The DMC also supports the protocol changes with this amendment that enables Age Group 3 patients who turn 1 year old during Part 2 of the study and who are safely tolerating the LCZ696/placebo 2.3 mg/kg bid dose, to be able to up-titrate to LCZ696/placebo 3.1 mg/kg bid dose (the target dose for Age Group 2), if it is in the patient's best interest as assessed by the Investigator.
- Based upon agreement with the EMA/PDCO (PIP M04) to align the age groups with the ICH E11 guidelines on pediatric subsets, modified age groups that will be included in the analysis.
- The enrollment target of 25% ACEI/ARB naïve patients has been removed, as it is considered not attainable given that patients in this study population are often initially treated with some form of RAS inhibition when first diagnosed. Ninety percent (90%) of the patients have been randomized thus far and only a small percentage (approximately 5%) of these patients are ACEI/ARB naïve.
- The requirement to include 20% randomized patients per age group in the analysis of Part 2 has been removed. Given the challenges of recruiting patients 1 month to <1 year old (Age Group 3), it is considered not feasible to enroll 72 patients (20% of 360 patients) in this age group. The requirement for 80 patients with an event in Category 1 or 2 has also been removed. The study is sufficiently powered based on the Global Rank Endpoint and the number of patients expected to have a Category 1 or 2 event.
- Patients in Age Group 2 will be required to be Ross class II or higher at randomization. This is based on the lower event rate observed in Age Group 2 patients vs. Age Group 1 patients.
- Measurement of height has been clarified with a statement recommending use of a stadiometer for standing height measurements.

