Dose levels for pediatric formulation	Valsartan total daily dose	Losartan total daily dose	Candesartan total daily dose
Dose level 1	0.7 mg/kg	0.4 mg/kg	0.2 mg/kg
Dose level 2	1.4 mg/kg	0.7 mg/kg	0.25 mg/kg
Dose level 3	2.0 mg/kg	1.0 mg/kg	0.32 mg/kg
Dose level 4	2.7 mg/kg	1.4 mg/kg	0.64 mg/kg
Dose levels for adult formulation	Valsartan total daily dose	Losartan total daily dose	Candesartan total daily dose
Dose level 1	40 mg	25 mg	4 mg
Dose level 2	80 mg	50 mg	8 mg
Dose level 3	160 mg	75 mg	16 mg
Dose level 4	320 mg	100 mg	32 mg

For age groups 1 and 2, the target dose for enalapril is 0.2 mg/kg bid (0.4 mg/kg total daily dose) with a maximum dose of 10 mg bid (20 mg total daily dose). For age groups 1 and 2, the target dose for LCZ696 is projected to be 3.1 mg/kg bid. Based on the PK/PD results from Part 1 for Group 3 patients, the target dose for LCZ696 (dose level 4x) will be 2.3 mg/kg bid. In addition, for Group 3 patients who turn 1 year old during the study, consideration should be given to uptitrate to a dose of 3.1 mg/kg bid (dose level 5x). See Appendix 14 for details. The LCZ696 dose is not to exceed 200 mg bid irrespective of the body weight (Table 3-5, Table 3-6). The actual target dose (dose level 4 or 4x, depending upon age group) and lower dose levels (1, 2, 3 or 1x, 2x, 3x, depending upon age group) of LCZ696 for Part 2 were determined based on PK and PD results from Part 1 of the study.

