#### 5.2 Treatment arms

Part 1 (PK/PD): All patients will receive open-label LCZ696. Patients completing Part 1 and who are willing to participate in Part 2 will be provided open-label enalapril (or their standard of care HF regimen) by the study site.

Part 2 (Efficacy): Patients are assigned to one of the following two double blind treatment arms in a ratio of 1:1 at the randomization Visit 401:

- LCZ696
- Enalapril

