# 5.3 Treatment assignment and randomization

At Visit 401, all eligible patients will be randomized via Interactive Response Technology (IRT) to one of the treatment arms. Patients will be stratified by age group (Age Groups 1, 2 and 3) and NYHA/Ross class group (Class I/II, Class III/IV) at randomization to ensure a balanced distribution of treatment allocation within each age strata. The Investigator or his/her delegate will contact the IRT after confirming that the patient fulfills all the inclusion/exclusion criteria. The IRT will assign a randomization number to the patient, which will be used to link the patient to a treatment arm and will specify a unique medication number for the first package of study drug to be dispensed to the patient. The randomization number will not be communicated to the caller.

The randomization numbers will be generated using the following procedure to ensure that treatment assignment is unbiased and concealed from patients/subjects and Investigator staff. A patient randomization list will be produced by the IRT provider using a validated system that automates the random assignment of patient numbers to randomization numbers. These randomization numbers are linked to the different treatment arms, which in turn are linked to medication numbers. A separate medication list will be produced by or under the responsibility of Novartis Drug Supply Management using a validated system that automates the random assignment of medication numbers to packs containing the investigational drug(s).

The randomization scheme for patients will be reviewed and approved by a member of the Randomization Group.

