The projected event percentages presented in Table 9-1 are based on the 8 month treatment period estimates. For a 52 weeks treatment period (Table 9-2), for Categories 1 and 2, the anticipated events percentages are calculated based on an exponential distribution assumption, extending from Month 8 to Month 12; and the remaining percentages within each treatment group are shared by Categories 3, 4, 5 according to their corresponding proportions at Month 8 (i.e. according to Table 9-1, 9:11:64 for the LCZ696 group, and 14:13:51 for the enalapril group). The treatment difference represented in Table 9-2 represents a Mann-Whitney-Wilcoxon Odds of 0.753.

Category	LCZ696 (%)	Enalapril (%)
Clinical event – death / heart transplant listing / mech. support	9	13
2. Clinical event – WHF	15	19

Worsened functional class: NYHA/ Ross Classification or worsened PGIS

	8.1	12.2

 
Unchanged functional class: NYHA/ Ross Classification and unchanged PGIS
 
	10.0	11.3

Improved functional class: NYHA/ Ross Classification or Improved PGIS

	57.9	44.5

The primary efficacy analysis will be a stratified Wilcoxon rank-sum test with alpha level of 0.05%, (two-sided). For the analysis of an ordered categorical endpoint with an underlying distribution as presented in Table 9-2, there is approximately 70% power with a sample size of 177 patients per group (354 total patients). Sample size calculations for the ordered categorical test (ordered categorical Mann-Whitney/Wilcoxon rank sum test) were determined using nQuery. Using a global ranked endpoint, the power under the same assumptions is expected to increase. While the exact increase in power is dependent on the distribution of the ranking within each category, simulation studies have demonstrated that the power for the global rank endpoint increases 10-20% more than with the ordered categorical analysis when the power of the ordered categorical endpoint is more than 50% (Sun 2012). Based on the assumptions stated, the power is estimated to be at least 80% for this study.

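### The primary and secondary models are stratified by age groups that differ from those used at randomisation, and the Cox and ordinal models also drop the class stratum: a small loss of precision, cheap to repair

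*Protocol*

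**What the plan says.** **Randomisation.** Protocol Section 5.3: "Patients will be stratified by age group (Age Groups 1, 2 and 3) and NYHA/Ross class group (Class I/II, Class III/IV) at randomization". The cut points are 1 and 6 years. Section 4 says the same, and Section 5.2 gives allocation "in a ratio of 1:1 at the randomization Visit 401".

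**Primary test.** Section 9.4.2 specifies a stratified Wilcoxon rank-sum analysis, "stratifying by modified age group (Group 1: 6 to < 18 years; Group 2a: 2 to < 6 years", with Group 3a running from 1 month to under 2 years, and by class group. The lower cut point is therefore 2 years.

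**Secondary models.** Section 9.5.1 stratifies the Cox model and the cumulative-odds models for NYHA/Ross and PGIS by modified age group only. The ordinal models carry the baseline value of their own outcome as a covariate.

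**Stated reason.** The Amendment 5 rationale cites an agreement with EMA/PDCO to follow the ICH E11 age subsets, giving "modified age groups that will be included in the analysis".

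**Other analyses.** Section 9.4.2 adds descriptive counts by both age systems. Section 9.4.4 repeats the primary model in the per-protocol set and adds off-treatment data for patients affected by the urgent safety measure. Section 9.4.5 plans a stratified test on the five categories without naming its strata.

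**The concern.** Group 3a joins every infant randomised in Group 3 with the 1 to <2 year part of Group 2. These two sets came from different randomisation strata and have separate dose tables in Section 3.1. For infants, "the target dose for LCZ696 (dose level 4x) will be 2.3 mg/kg bid", while the LCZ696 target for Groups 1 and 2 is 3.1 mg/kg bid.

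Stratified randomisation gains precision when the analysis conditions on the same factors. If infants and one-year-olds differ in prognosis, merging them puts that difference into the error term. Arm balance among one-year-olds is also no longer controlled within their analysis stratum. The secondary models go further, because they omit class group, a randomisation factor.

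Precision is at stake, as is agreement between the design and the analysis. Control of the type I error is not.

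**Working it through.** **1. The plan's own power figure.** Inputs: Table 9-1, Table 9-2, "The overall significance level (Type 1 error) of 0.05 (2-sided) will be used", 177 per group.
- Categories 1 and 2 at 12 months are 1 − (1 − p)^1.5. LCZ696: 6% → 8.86%, 10% → 14.62%. Enalapril: 9% → 13.19%, 13% → 18.85%. Rounded, these are the 9/15 and 13/19 of Table 9-2.
- θ = P(LCZ696 better) + ½P(tie) = 0.5705, so (1 − θ)/θ = 0.4295/0.5705 = 0.753. The plan says the difference "represents a Mann-Whitney-Wilcoxon Odds of 0.753".
- Tie-corrected null variance = (1 − Σp̄³)/12 × 2/n, with p̄ = 0.110, 0.170, 0.1015, 0.1065, 0.512 and Σp̄³ = 0.1427. This gives 0.8573/12 × 2/177 = 0.000807, SE 0.0284. Then 0.0705/0.0284 − 1.96 = 0.52, a power of 69.9% (70.4% by simulation).
- The plan says "there is approximately 70% power with a sample size of 177 patients per group (354 total patients"). It reproduces. At 180 per group the categorical test has 70.8%. The stated 80% relies on a cited gain from full ranking, which I did not test.

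**2. Size and power under each set of strata.** The age mix and prognostic gaps are not in the documents, so I assumed ranges. Set-up: N = 360, 1:1 permuted blocks of 4 within the six randomisation strata, 15% in class III/IV with a class effect of −0.8 on the logistic scale, and a treatment shift of 0.52 for about 80% power. The test was a stratified Mann-Whitney with weights n₁n₂/(n₁+n₂), 4,000 trials per row. Age mix is in the order 6-<18, 2-<6, 1-<2, <1 y. Age effects in that order are none; moderate (0, 0.5, 0, −0.7); strong (0, 1, 0, −1.5).

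| Age mix (%) | Age effect | Randomised strata | Modified age × class | Nested ages × class | Modified age only |
|---|---|---|---|---|---|
| 60/20/12/8 | none | 81.0 | 81.0 | 80.7 | 80.4 |
| 60/20/12/8 | moderate | 80.3 | 80.1 | 80.0 | 79.9 |
| 60/20/12/8 | strong | 78.8 | 77.9 | 79.1 | 77.1 |
| 45/20/20/15 | none | 81.0 | 80.9 | 80.6 | 80.5 |
| 45/20/20/15 | moderate | 80.6 | 80.2 | 80.5 | 79.4 |
| 45/20/20/15 | strong | 78.4 | 77.5 | 79.6 | 77.1 |

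Randomised minus modified strata: 0 to 0.9 points. Randomised minus modified age only: 0.4 to 1.7 points. Type I error was 4.9-5.4% (randomised), 4.5-5.6% (modified) and 4.2-5.4% (modified age only), with a Monte Carlo SE of about 0.3 points. The last column is a rank test, so it only indicates what the Cox and ordinal models lose.

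**3. A harsher set.** Van Elteren test, N = 360, blocks of 4, 3-8% infants, 15% aged 1-<2 y, 22% aged 2-<6 y.
- With 3% infants, the gain from randomised strata was −0.7 to +1.1 points.
- With 8% infants, 0 to 0.5 SD worse, it was −0.5 to +0.9.
- With 8% infants, 1 SD worse, and one-year-olds at 0 to +0.5 SD, it was 1.7 to 2.4. The largest gain in any run was 2.7.

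**4. Imbalance.** In these runs the arm difference in the under-2 stratum averaged 5 patients, with a 95th percentile of 11-12. The stratum holds at least (3% + 15%) × 360 ≈ 65 patients. Information relative to an equal split is 1 − (d/n)². The loss is (5/65)² = 0.6% on average and (12/65)² = 3.4% at the upper end, in that stratum alone.

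**5. How many infants.** Amendment 5, which opened Part 2 to infants, reports about 325 enrolled. Amendment 7 reports 375 randomised and treated. Infants are therefore at most about 50 (50/375 = 13%). Amendment 6, at about 335, describes Part 2 recruitment as ongoing in Groups 1 and 2 only, which suggests at most about 40 (11%).

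**6. Sparse cells.** At 15% class III/IV, 3% infants give 360 × 0.03 × 0.15 ≈ 1.6 such patients, and 8% give ≈ 4.3. In simulation, some infant-by-class cell had at most one patient in an arm in about 92% and 37% of trials.

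**The case against.** The strongest reply is that the change is open, pre-specified and made on a baseline variable, with a stated regulatory reason. Amendment 5 adds the groups to the analysis itself, so it would be wrong to say that no reason is given or that they were meant only for reporting. This stands. What the rationale leaves unexplained is why the randomised strata then drop out of inference altogether.

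A reader might infer that analysing across randomisation strata invalidates the test. It does not: each modified stratum still compares randomised arms, and simulated size is about 5%. A reader might also infer that pooling two dose schedules biases the result. Both arms follow parallel dose levels, and infants who turn 1 may move to the level used in Group 2 (Section 3.1, Appendix 14). The difference in target dose bears on how a Group 3a result is read, not on the validity of the test.

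Nor can one conclude that no randomised-strata analysis exists. The supplied SAP is a regional supplement for Chinese and East Asian populations that defers to a main SAP not supplied here.

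Two practical objections also stand. Splitting infants by class leaves very small cells. And at Amendment 7, 339 of 375 patients had completed or discontinued, so replacing an agreed primary test is a protocol change.

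**Conclusion.** The mismatch is real but minor. For the primary test it costs about 0 to 1 point of power, and 2 to 3 points only if infants do much worse than one-year-olds. The documents do not establish that gap: the lower event rate that Amendment 5 reports is for Group 2 against Group 1, a boundary both age systems keep. The clearer case is the secondary models, which omit a randomisation factor. On a rank test the corresponding loss was 0.4 to 1.7 points. The NYHA/Ross model is largely exempt, because baseline class is already its covariate. All power figures rest on the assumed age mix, class split, block size and prognostic effects. The planned sample size is unaffected.

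**What to change.** Make these changes before unblinding, in the SAP amendment that Appendix 15 already announces:

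1. Stratify the Cox and ordinal models by the randomisation factors, age group and NYHA/Ross class group. For the NYHA/Ross model only the age factor needs to change.
2. Run the primary rank test on the randomised strata, or on nested ages (<1, 1-<2, 2-<6, 6-<18 y) by class, so that each analysis stratum lies inside one randomisation stratum. If the agreed modified strata must stay primary, pre-specify the randomised-strata analysis as a sensitivity analysis and state the reason for the departure.
3. Pool an infant age-by-class cell across class when either arm has fewer than two patients. Pooling only when an arm is empty would keep one-patient cells, which give no within-arm variance.
4. Keep the modified age groups for subgroup and descriptive tables.

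If the main SAP already contains such an analysis, only the protocol wording needs to be aligned. The cost is a changed strata variable, a protocol wording change, one extra analysis and some sparse infant cells. No new data are needed.
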